1.3.2 Criteria for selection of subjects

1.3.2.a: Inclusion criteria for providers and sites

Physicians (specializing in either Obstetrics/Gynecology or Family Medicine), nurse practitioners, and other advanced practice clinicians who provide medical abortion services and routinely use TVS prior to medical abortion are eligible for this study. All clinics selected for this study currently provide medical abortion up to 70 days from LMP. Our study will not require any change to current protocols used at these clinics when scheduling patients for medical abortion. All clinics use clinical charting (either EMR

or paper charts) which have pre-specified templates from which relevant data can be extracted, including all tests that have been ordered or performed.

1.3.2.b: Exclusion criteria for providers and sites

Providers who do not provide medical abortion services are not eligible.

1.3.2.c: Inclusion criteria for patients

Eligible patients include English- or Spanish-speaking women seeking medical abortion, 18 years or older. They will be at an estimated gestational age up to 70 days from LMP.

1.3.2.d: Exclusion criteria for patients

We will exclude women under 18 years old. Since parental consent is required for participation in research, inclusion of younger women could impair patient confidentiality. There are otherwise no study-specific exclusion criteria. If after enrollment, a woman proves to be at too advanced a gestational age for medical abortion (>70 days from LMP), elects aspiration abortion, has an ectopic pregnancy, or has an early pregnancy failure, she is still eligible for participation and will be included in the analysis.

1.3.3 Subject recruitment and allocation

Please see Table 2 for specific characteristics of proposed study locations, including details of each site's capacity and providers. These sites may change depending on workflow and patient volume. We plan to start enrollment at one CUMC site and one PPCGNNJ site; both sites are diverse in both patient and provider types. Once these sites are well-integrated, we will decide if we need to add more clinics to bolster participation and enrollment. We plan to include more sites as needed based on needed sample size and recruitment rate.

We will randomize patients to the type of ultrasound using a 1:1 ratio, stratified by site, with half of the participants at each site being randomized to receive TAS, and half to receive TVS. Block size will be created using simple randomization; block size will vary between 4 and 6. An investigator experienced with generating randomized sequences and not directly involved in this study will be responsible for creating the entire randomization schedule; first, by defining the sequence of block sizes and second, by defining the assignments within each block. Most of the fellows in the last decade in this division have carried out randomized trials as part of fellowship projects and thus division staff has substantial experience in generating the lists. The central research office at CUMC will prepare opaque, sealed envelopes containing cards indicating whether a given patient has been randomized to receive either TVS or TAS. These envelopes and cards will be sequentially numbered, corresponding to site, and sequentially numbered study enrollment logs. The allocation will remain concealed from the sonographer as well as the participant and provider until the coordinator provides the ultrasound randomization envelope to the sonographer, following the consent and enrollment process. The sonographer will open the sealed, opaque envelope immediately prior to the ultrasound examination, which will then be performed according to randomization assignment.

There will be no blinding. Even if the clinician providing care does not perform the ultrasound, by viewing the image and interpreting the results they would immediately be able to see if TVS or TAS was performed. It is also not feasible to blind study participants to the type of ultrasound being performed. A study in which participants undergo both types of US, but the clinician uses only one for clinical decision making would be possible, but would not improve on the planned study.

1.3.4 Description of the drugs and devices to be studied

All clinics participating in this study provide medical abortion using the evidence-based regimen of mifepristone and misoprostol. This includes mifepristone 200 mg orally on day 1 in the office, followed by misoprostol 800 mcg buccally 24-48 hours later, at home. Mifepristone, or Mifeprex, is manufactured by Danco Laboratories, LLC ([name]). There are multiple manufacturers of misoprostol; at CUMC by Greenstone, LLC ([name]), and at Planned Parenthood of Greater and Central New Jersey by Novel Laboratories, Inc. ([name]).

1.3.5 Admission procedure

The clinician in charge of clinic operations for a given patient care session will review their schedule and identify patients for potential enrollment, or they may delegate identification to an onsite study coordinator. The study coordinator will then approach all eligible patients and if the patient is interested and agrees to participate, obtain informed consent. Participants will undergo the assessment as described in section 1.3.1.e.

1.3.6 Follow-up procedure

This is a single-day study; follow-up evaluation of medical abortion is not a specific aim of this study and all participants will follow-up with their provider per each site's individual protocol. For example, at CUMC, enrolled participants will return for a repeat ultrasound and physical exam in 1-2 weeks to assess completion of medical abortion. For those patients who do not receive an abortion on the day of study enrollment, study coordinators will perform follow-up chart abstraction to ascertain eventual outcome (i.e. abortion performed at later date, surgical abortion performed, patient elected to continue pregnancy, ectopic pregnancy diagnosed, etc.). Study coordinators will also perform chart abstraction to record details about any additional testing ordered and final clinical outcome as available two weeks from the time of the enrollment visit.

1.3.7 Criteria for discontinuation

1.3.7.a: Provider component

Providers may choose to discontinue participation in this study at any point. We anticipate overall participation to last for at least four months and for at most eight months for each provider.

1.3.7.b: Patient component

Patients can withdraw from the study at any point. The duration of the study for each patient may vary; the patient may be present in the clinical environment for several hours from registration to discharge. However, study-specific activities for each participant will last no more than 1-2 hours.

1.3.8 Laboratory and other investigations

All women seeking abortion who are involved in this study will undergo a routine evaluation as part of routine care. This will begin with intake per clinic routine, followed by history, physical examination (vital signs, abdominal exam), and then either TVS or TAS depending on randomization. We will compensate clinical sites for the cost of additional testing beyond their usual practice in the group randomized to receive TAS, under the assumption that this group will undergo additional testing due to study participation, compared to those who receive TVS.

Ultrasound machines and HLD systems vary by site. At Planned Parenthood and CUMC, providers utilize the LOGIQ P5 ultrasound manufactured by GE Healthcare. Planned Parenthood will be utilizing the Trophon EPR HLD system manufactured by GE Healthcare and CUMC utilizes Cidex OPA, manufactured by ASP.

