Women who present for medical abortion will be eligible for this study, and will undergo a routine evaluation including relevant history, abdominal examination, and randomization to receive either TVS or TAS. Following evaluation, providers will make a clinical decision regarding the patient's eligibility for medical abortion, and will proceed with usual care. We will evaluate the proportion of women in the TVS and TAS groups for whom providers ordered additional testing or additional visits prior to making a decision regarding eligibility.

Our primary study outcome will be the proportion of women whose clinician orders additional evaluation after sonography and prior to determination of medical abortion eligibility. We hypothesize this proportion will be greater among those randomized to TAS (non-inferiority boundary of 80%). That is, if clinicians order additional testing in less than 20% of women undergoing TAS, we will consider TAS to be non-inferior to TVS.

Our second major outcome will be patient satisfaction after ultrasound examination. We hypothesize satisfaction will be greater among those randomized to TAS. Following study activities, each participant will complete a satisfaction questionnaire regarding the type of ultrasound she received (TVS or TAS) using a visual analog scale (VAS) and be asked, if she were to require an ultrasound in the future, which she would prefer.

The results from this study could demonstrate that when TAS is used, clinicians order additional testing in a greater proportion of patients than when TVS is used. However, we hypothesize this difference in proportions will fall within a non-inferiority boundary of 80%. Although we expect a difference, we anticipate that this difference in proportions will not be so large that using TAS instead of TVS will be burdensome to providers, clinics, or patients. Many providers in the US already have TVS capabilities and HLD, and may desire to continue using this tool. For such providers, however, switching from TVS to TAS for most patients could reduce costs and increase patient satisfaction. For potential providers who do not have TVS capabilities, our results will help to estimate how often TAS would be sufficient to provide care versus how often patients might need a referral for additional testing.

1. Description of the project

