1.3 Design and methodology

1.3.1 Research design and general methodological approach

This will be a randomized controlled trial comparing TAS to TVS in medical abortion eligibility assessment. With this trial, we aim to improve healthcare processes under real-world conditions at specific clinics where providers now routinely use TVS prior to medical abortion. We will consult the SPIRIT (Standard Protocol Items: Recommendations for Interventional Trials) 2013 guidelines^{69,70} and the CONSORT guidelines, specifically the Practihc (Pragmatic Randomized Controlled Trials in Health Care) reporting guidelines.^{71,72,73} Study protocols will closely match usual care at these sites to help ensure high generalizability of the results of this pragmatic trial.

To evaluate clinician practices at different sites, we plan to enroll women at a hospital-based clinic system (including sites serving Medicaid patients and a faculty practice serving commercially insured patients), and one Planned Parenthood affiliate. Sites will vary in location, ranging from urban clinics to large suburban practices. This will provide diverse study participants and providers. Please see Table 2 (in appendix) for further details on each potential site. Currently, these sites routinely perform TVS before medical abortion.

1.3.1.a: Sites

We will enroll participants at Columbia University Medical Center (CUMC) and Planned Parenthood of Central and Greater Northern New Jersey affiliate (PPCGNNJ). We met with [name], Vice President of Research Development at PPCGNNJ, to discuss our proposed study at length and visited these clinics. Clinics affiliated with CUMC and PPCGNNJ have relevant research experience, including randomized controlled trials and abortion research.

1.3.1.b: Participants

Study participants will include women with an estimated gestational age up to 70 days based on LMP, who desire medical abortion and present to any of our study sites for care. Study participants will complete a questionnaire regarding demographic information as well as experiences with abortion, including medical abortion specifically, delivery, miscarriage, TAS, and TVS. Further inclusion and

exclusion criteria are listed below in section 1.3.2. Study forms will not include any personal identifiers and all participants will be assigned study identification numbers to protect confidentiality.

1.3.1.c: Training, Study Coordinators

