1.3.12 Study limitations

Our project is a randomized controlled trial that will aid us in better answering the question of whether TAS provides sufficient information or changes the need for further testing to determine medical abortion eligibility, when compared to TVS. Providers' judgment still may have an important effect on our clinical outcomes, however, our endpoint is whether the provider orders a test or not.. Subjectivity is certainly possible, even likely, but our design replicates the real-world healthcare setting in which providers currently routinely use TVS. We are using the PractiHC extension to the CONSORT guidelines to assist us in designing this study in a way that will provide useful information for our health-services study question.

We anticipate possible differences in outcomes based on provider type and experience. For this reason, we are attempting to include a variety of providers and analyze these differences, as discussed above. We may have difficulty enrolling a sufficient number of patients for certain provider types (such as family physicians) to demonstrate any real differences in proportions between groups and are therefore not basing our power calculations on such planned analyses. We visited multiple family medicine clinics in preparation for this study, but ultimately excluded these study sites due to low medical abortion volume. Additional details regarding practice volume at proposed study sites within CUMC and PPCGNNJ are included in Table 1.

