Appendix:**Table 1: Potential additional testing ordered by providers**

 • Additional visit (within 1 week) for reassessment • TVS (performed following TAS on the same day of service or at the additional visit) • Pelvic examination (bimanual) • Quantitative serum β-hCG levels • Urine pregnancy test • Diagnostic aspiration procedure • Referral for urgent evaluation (i.e. at an urgent care center or the emergency department) • Other methods not listed here

Table 2: Proposed Research Sites

Clinical Site		Clinic Type	Providers	Insurance	Setting	Average med ab volume/month
CUMC	VC10	Hospital-based	3 O/G 1 FM	M	Urban	30
	[name]	Private practice	4 O/G	C/S	Urban	8
	Farrell	Hospital-affiliated	2 FM	M	Urban	8
PPCGNNJ	Elizabeth	Free-standing clinic	3 O/G 1 FM 1 NP	M/C/S	Urban	80
	Hackensack		1-3 NP	M/C/S	Suburban	60
	Morristown		1 NP 3 O/G	M/C/S	Suburban	50
	Trenton		1-3 NP	M/C/S	Urban	30
Total	Up to 7 available sites ¹		21-25 (13 O/G, 4 FM, 4-8 NP)			266

Key: O/G = Obstetrician/Gynecologist physician, FM = Family Medicine physician, M = Medicaid insurance, C = Commercial insurance, NP = Nurse Practitioner, S = self-pay.

¹Not all sites will be used in the study unless otherwise indicated, e.g. for improved enrollment/recruitment.

References:

¹ Pazol K, Creanga AA, Jamieson DJ. Abortion surveillance—United States, 2012. Morbidity and Mortality Weekly Report, 2015, Vol. 64, No. SS-10.

² Finer LB, Wei J. Effect of mifepristone on abortion access in the United States. Obstet Gynecol 2009;114:623-30.

-
- ³ Jordan B, Shields WC. Happy anniversary mifepristone: a decade of promises and challenges. *Contraception* 2010;82(3):219-20.
- ⁴ Boonstra HD. Mifepristone in the United States: status and future. *Guttmacher Rep Public Policy* 2002;5:4-7.
- ⁵ Guttmacher Institute, State policies in brief: requirements for ultrasound as of September 1, 2015, 2015, <http://www.guttmacher.org/statecenter/spibs/spib_RFU.pdf>, accessed Sep. 4, 2015.
- ⁶ Guttmacher Institute, Laws affecting reproductive health and rights: 2014 state policy review, 2014, <<http://www.guttmacher.org/statecenter/updates/2014/statetrends42014.html>>, accessed Sep. 4, 2015.
- ⁷ Raymond E, Grossman D, Wiebe E, Winikoff B. Reaching women where they are: eliminating the initial in-person medical abortion visit. *Contraception* 2015;92:190-3.

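### Compensation for additional testing is described for the TAS arm only, in an unblinded trial whose primary endpoint is the order for additional testing

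*Combined protocol and SAP*

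**What the plan says.** Section 1.3.8 sets out the payment: "We will compensate clinical sites for the cost of additional testing beyond their usual practice in the group randomized to receive TAS". The reason given is "under the assumption that this group will undergo additional testing due to study participation, compared to those who receive TVS". No provision for the TVS group appears anywhere in the protocol.

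The other relevant statements are these:

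- **Endpoint.** Project summary: "Our primary study outcome will be the proportion of women whose clinician orders additional evaluation after sonography and prior to determination of medical abortion eligibility". Section 1.3.12 puts it more briefly: "our endpoint is whether the provider orders a test or not".
- **Masking.** Section 1.3.3: "There will be no blinding".
- **Discretion.** Section 1.3.12: "Subjectivity is certainly possible, even likely, but our design replicates the real-world healthcare setting in which providers currently routinely use TVS".
- **What counts.** Appendix Table 1 lists the qualifying tests. A TVS done after TAS, on the same day or at an extra visit, is one of them.
- **Pragmatic aim.** Section 1.3.1: "Study protocols will closely match usual care at these sites to help ensure high generalizability of the results of this pragmatic trial".

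**The concern.** The clinician knows the arm and decides whether to order a test, and that decision is the outcome. The study covers the cost of extra tests in one arm. The tests that may be paid for can be the same tests that are counted as events. The conditions under which an event arises may therefore differ by arm for a reason unrelated to what the scan shows.

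If that happened, the TAS rate and the TAS-minus-TVS difference would combine the performance of the scan with the effect of the payment. Two aims would suffer. The non-inferiority comparison could fail when TAS is in fact acceptable. The estimate of how often TAS suffices, which the project summary offers to clinics without TVS, would be too pessimistic, because those clinics will have no study reimbursement.

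The protocol describes no safeguard: no common payment rule for both arms, no separation of ordering clinicians from the payment, no prespecified criteria for ordering, and no masked review of orders. The limitations in section 1.3.12 do not mention the payment.

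**Working it through.** **Inputs** (section 1.3.11, Table 3, row 1): additional testing 5% after TVS and 10% after TAS; margin 10 points; one-sided alpha 0.05; power 80%; 340 per arm. The project summary plans about 800 women, or about 400 per arm at 1:1.

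**Reproducing the plan's figure** (unpooled variance):

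n = [p1(1−p1) + p2(1−p2)] × (z0.95 + z0.80)² / (margin − (p2 − p1))²

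= (0.0475 + 0.0900) × (1.645 + 0.842)² / (0.10 − 0.05)² = 340.04

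This agrees with the stated 340, so the sample size rests on a 10-point margin.

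**Sensitivity.** The size of any payment effect is not in the documents. As an assumption, TAS ordering rises by a few points and TVS stays at 5%.

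Power = Φ[(margin − (p2 − p1)) / SE − 1.645], with SE = √{[p1(1−p1) + p2(1−p2)] / n}

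Worked case, n = 340, TAS 11%, 10-point margin: SE = √[(0.0475 + 0.0979)/340] = 0.0207; 0.04/0.0207 − 1.645 = 0.29; Φ = 0.614.

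The margin needs two values. Table 3 pairs a 10-point margin with an 80% boundary. Measured from the assumed TVS rate, 95% − 10 points is 85%, whereas 95% − 80% is 15 points. That inconsistency is a separate matter, but it decides how much the payment could matter.

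| Rise in TAS ordering | 10-point margin, n = 340 | 10-point margin, n = 400 | 15-point margin, n = 340 |
|---|---|---|---|
| 0 | 80.0% | 85.4% | >99.9% |
| 1 point | 61.4% | 67.5% | 99.7% |
| 2 points | 40.9% | 45.6% | 98.3% |
| 3 points | 23.4% | 25.9% | 94.2% |
| 5 points | 5.0% | 5.0% | 71.2% |

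**Is it the one-sidedness that matters?** If ordering rose equally in both arms, power at 340 per arm with the 10-point margin would be 75.9% for 1 point and 72.1% for 2 points. A rise confined to the TAS arm costs far more.

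**Extra reimbursed evaluations if TVS were also covered:** 0.05 × 340 = 17, up to 0.075 × 400 = 30, using the 5–7.5% base assumption in section 1.3.11.

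**The case against.** The strongest reply is that the incentive is inferred rather than documented. The payment goes to sites, not to clinicians, and covers only costs beyond usual practice. It can remove a deterrent but creates no profit. Nothing says that ordering clinicians know of it, or that cost normally holds them back; Table 2 shows a mix of Medicaid, commercial and self-pay patients. All of this stands, and it is why the point is conditional on clinicians knowing.

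A second reply is that the clause may neutralise a distortion. The study replaces routine TVS with TAS and expects more follow-on tests. Without compensation, sites would carry a study-caused cost in the TAS arm alone, which might discourage ordering there and favour non-inferiority. This also stands, and it argues for keeping compensation in some form.

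Third, any bias works against the sponsor's hypothesis. That is correct for the non-inferiority test, but it does not help the estimate of how often TAS is sufficient.

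Fourth, the word *only* rests partly on silence: the clause does not expressly exclude TVS. The stated reason does contrast the two arms, however, so the one-arm reading is the natural one.

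A reader might infer from the power figures that the payment leaves the trial seriously underpowered. The documents do not support that. The 1- and 2-point rises are assumptions, and the large losses arise only with the 10-point margin. Under the project summary's literal rule of TAS testing below 20%, tested one-sided at 5% with 340 women, power at a true TAS rate of 12% is still 99.8%.

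**Conclusion.** The concern holds in a limited form. The payment is described for one known arm, the endpoint is a discretionary order, and no safeguard is given. If ordering clinicians are aware of the payment, the likely direction is more ordering after TAS, so the TAS rate and the difference would be biased upward and non-inferiority would be harder to show.

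The size is unknown. Under the assumed rises the effect on power runs from serious (10-point margin) to negligible (15-point margin). Any upward bias in the estimates would be present under either margin.

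Two stronger readings should be resisted. One is that clinicians are paid to order tests; the text speaks of sites and of cost recovery. The other is that the payment could produce a false claim of non-inferiority; more ordering after TAS does not inflate the type I error. The case for acting is that the safeguard costs almost nothing, not that harm to the result has been shown.

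**What to change.** 1. Amend section 1.3.8 to say who is paid, for which Table 1 items, and when. Pay the site in aggregate, for example retrospectively or as a flat per-participant amount in both arms.
2. State that the payment will not be communicated to ordering clinicians as tied to TAS assignment.
3. Add the arrangement to the limitations in section 1.3.12, with the expected direction of bias.

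For retrospective aggregate payment, the cost is a change of wording in the protocol and site agreements. A flat amount in both arms would need a budget estimate, because the documents give no test prices.

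*Optional:* reimburse additional evaluation by the same rule in both arms. This removes the asymmetry directly, at about 17 to 30 further reimbursed evaluations. The drawback is that TVS is the usual-care comparator, so paying for its follow-on tests departs somewhat from usual care and could raise the rate the trial is meant to observe. For that reason it is an alternative to weigh and not the main recommendation.

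None of these changes affects which tests a clinician may order.
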